# 8.4. Consent.

Regardless of recruitment approach used, signed informed consent will be obtained at the measurement visit, prior to obtaining measurements. Participants will be provided ample time to review the consent form. An investigator or study staff person will view each section with the participant, ask the participant if they understand each section, and clarify any questions they may have. The participant and the person obtaining consent will sign and date the consent form. A copy of the consent will be placed in the participant's medical record. Informed consent will be considered an ongoing process throughout the study, and participants' questions regarding their rights and responsibilities will be addressed whenever they occur. Participants will be paid \$50.00 for each of the 2 measurement visits as compensation for their time. Participants will be reimbursed \$5.50 for roundtrip travel should they need to return for FGM replacement.

# 9.0. Study Timelines

We will recruit approximately 5 cohorts of 4 participants each for the sample size of 20 participants. A new cohort will be randomized approximately every 4 weeks. The maximum number of study participants at any point in the study will be 10.

# 10.0. Study Endpoints

We will validate the PNP algorithm for North American T2D and pre-diabetes patients in a 2-stage, repeated measures quasi-experimental trial in which participants serve as their own control. In stage 1, PNP methods will be used to conduct metabolic profiling and develop a patient-specific algorithm that predicts glycemic responses to food (iAUCpred). In stage 2, participants will consume, for 6 days, isocaloric diets (breakfast, lunch, dinner, and 2 snacks), which will be prepared and delivered daily, including 2 days each of low, moderate, and high glycemic load (GL) foods.

**10.1. Specific aim 1.** We will characterize iAUCpred and iAUCobs and describe differences between the two. Prior studies suggest that any difference between two AUCs less than  $\delta = 30\%$  of iAUCobs is not important and will be considered equivalent. Thus we will describe the equivalence of iAUCpred and iAUCobs by testing the null hypothesis of non-equivalence: H0:  $|iAUC_{pred} - iAUC_{obs}| \ge \delta$  and the alternative hypothesis of equivalence is H1: H0:  $|iAUC_{pred} - iAUC_{obs}| \le \delta$  overall and within each race/ethnicity. **10.2. Specific aim 2**. We will describe the extent to which the equivalence of iAUCpred and iAUCobs differs by whether or not the participant is prescribed metformin.

**10.3. Specific aim 3.** In preparation for future grant applications, we will establish the feasibility and acceptable of the research protocol.

## 11.0. Procedures involved

## 11.1. Stage-1 Metabolic Profiling

The study flow chart is given in the **figure-1** (appendix). The total duration of the study is approximately 4 weeks and includes 2 visits and 7 scheduled telephone calls. Two days prior to the eligibility visit, we will call the patients and remind them about the study (Telephone- **prescreen**). During the eligibility visit, participants will attend a measurement visit at the NIH-CTSI-funded Clinical Research Center (CTSI-CRC) (**visit-1**). During visit-1, prior to the blood draw, the study procedures will be reviewed with the participants and signed informed consent will be obtained. During the eligibility visit, we will draw 5 ml of fasting blood (~ 1 teaspoon) for the assessment their HbA1c. We will measure patients' resting energy metabolism in fasting state using indirect calorimetry (Quark RMR, COSMED USA Inc, Chicago II) with an activity modifier of 1.3, rounded up to one of the following daily energy expenditure levels (1600 kcal, 2000 kcal, 2400 kcal, 2800 kcal, 3200 kcal). The QUARK RMR is an open-circuit calorimeter for measurement of mechanically assisted patients and spontaneously breathing patients. We will use the conventional Mifflin equation for participants that are apprehensive of wearing a mask to undergo this procedure.

If the participants meets the inclusion criteria (HbA1c value of less than 8.0% then we will contact them include them for the study (Telephone-1). In advance of their appointment, participants will be mailed questionnaires and stool sample kit with directions for collection. They will bring their stool sample with them to the CTSI-CRC, at which time we will collect various measures required by the PNP algorithm. Participants will be contacted 2 days prior to their appointment (Telephone-2) to remind them of their profiling visit (visit-2). Researchers will review the questionnaires and clarify the questions related to the study. We will draw 15 ml of blood (~ 3 teaspoons) samples for the following blood tests:

- blood laboratory measures (complete blood count (CBC), biochemistry panel, serum albumin, C-reactive protein, ferritin, lipid panel, HbA1c, fasting insulin and glucose, alanine transaminase (ALT), aspartate transaminase (AST), thyroid stimulating hormone (TSH), serum creatinine)
- ✓ glycated albumin
- ✓ collect the anthropometric measurements (height, weight, waist circumference and body fat %)

Laboratory tests will be collected, spun, refrigerated, batched and sent for processing in the Clinical Laboratory Improvement Amendments (CLIA) certified NYU CTSI Translational Research Laboratories by personnel blinded to group assignment. A baseline questionnaire will be administered to collect various covariates, described below.

De-identified stool samples will be express-shipped to the Weizmann Institute, where microbiome features (16S rRNA and metagenomic relative abundance, KEGG pathway and module relative abundances and bacterial growth dynamics - PTRs) are extracted. The Weizmann Institute will combine these data with gut microbiome profiles and PNP app derived self-monitoring data to develop an individualized predictive model of glycemic response from which we will derive iAUCpred.

A professional, blinded, flash glucose monitoring (FGM) device will be inserted on the backside of each of your arms to measure interstitial glucose every 15 min (Abbott Sensor Based Glucose Monitoring System, Freestyle Libre Pro; Whitney, UK) for 14 days (**Day-1**). The sensor is calibrated in the factory and needs no calibration during the 14 day wear. We will load the PNP app on the participant's smart phone or study loaner smart phone and train them in its use. The PNP app records time-stamped entries pertaining to meals, physical activity, sleep, medications, hunger, and stress. Participants will be instructed to enter meals, medications, and stress into the PNP app in real time. Participants also will be provided with a Fitbit to capture continuous sleep and physical activity data over the next 7 days.

Subsequently, for the next 6 days, participants will be instructed to follow their normal daily routine and dietary habits, except for the first meal of every day (hereafter referred to as the "test meal".) Test meals consist of one of three different types of standardized meals – each consisting of 50 g of available carbohydrates, given twice to each participant (110 g white bread, 110 g white bread and 30 g of butter, 50 g glucose. Participants will be instructed to enter foods (test and other meals), and amounts consumed into the PNP app (**Day:2-Day:7**). Participants also will be instructed to wear a Fitbit device that streams data on physical activity and sleep to the participant's smart phone (by FitBit app). A follow-up phone call (Telephone-3) to the subject will be made by the study personnel to check that the subject has been able to use the Abbott FGM, PNP app without any issues and let the subject know that the test meals for the next 3 days (**Day:5-Day:7**) will be home delivered. Any adverse events or device incidents will be recorded.

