#### 11.2.2. Feeding study:

**Stage-2** feeding will take place on the 8th day Beginning the following day, for 6 days, participants will consume prepackaged meals and snacks. In order to limit the effects of meal order on glycemic response, each meal day will contain a random breakfast, lunch, dinner and 2 snacks from among those selected. The study personnel will call the subject on the 7th day to let the patient know about the feeding phase in detail (Telephone-4). Also, they will discuss about the feasibility and the barrier of using Abbott FGM, PNP app and FitBit. Also, the study personnel will ask the subject to charge the FitBit device. During stage-2 feeding phase, participants will continue to monitor meals, physical activity, sleep, medications, hunger, and stress with the PNP app. We also will obtain FitBit data on physical activity and sleep. A follow-up phone call (Telephone-5) to the subject will be made on to check that the subject is consuming the foods provided by the study and has been able to use the Abbott FGM without any issues. Any AEs or device incidents (DIs) will be recorded. To ensure that the glycemic response to meals and snack can be detected, participants will be directed to leave at least two hours between eating occasions. Although they will be asked to consume all foods and beverages provided, and nothing else (other than water for hydration), participants will be directed to record and report any deviation from the prescribed diet. On the day following the final meal, upon awakening (Day **14**), we will

Protocol version 02/23/2018 Study Protocol: s16-01059 NCT: NCT03053518 call the participants' (Telephone-**6**) and directed to remove the FGM, FitBit devices and return it to the investigators in a postage-paid sharps box provided to them. If the participants did not send the devices within 5 days after the study completion then we will call them 2 additional times (Telephone-**7** and Telephone-**8**).

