## 11.4. Analysis plan.

11.4.1. Outcome: Observed incremental area under the curve (iAUCobs) at 2 hours following each meal and snack will be evaluated via FGM using the Abbott Libre Pro, which captures interstitial glucose every 15 minutes. A sensor is inserted into the participant's arms. Participants will be blinded to glycemia tracings.

11.4.2. Covariates: Baseline characteristics. We will measure glycated albumin, a measure of glycemic control over a 2-3 week period. A questionnaire also will be administered to collect the following information:

- $\checkmark$  health characteristics of the participant and family members
- ✓ medication regimen
- general habits [dietary, sleep, physical activity, smoking, and bowel)]
  recent treatment with antibiotics
- ✓ birth history
- ✓ stress
- ✓ apnea risk

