#### 11.5. Data analysis:

A descriptive analysis of all data collected will be performed using appropriate graphical and numerical exploratory data techniques. Data transformations will be performed to account for non-normal distributions. We also will conduct sensitivity analyses pertaining to the effects of baseline medication regimen (use of metformin or not). To address privacy concerns around microbiome sequencing, we implement metagenomic analyses using secure computation using secureseg platform (https://github.com/HCBravoLab/MicrobiomeSC). The median PPGR to standardized meals for each participant with 16S rRNA relative abundance at the species to phylum levels, MetaPhIAn tag-level relative abundance and relative abundance of KEGG genes will be examined using the Pearson correlation. We will cap relative abundance at a minimum of 1e-4 (16S rRNA), 1e-5 (MetaPhIAn) and 2e-7 (KEGG gene). For 16S rRNA analysis, the taxa with <20% of the features will be removed. The information obtained from this preliminary investigation of the data will be used as follows.

Specific Aims 1 and 2. We will compare iAUCpred and iAUCobs overall, and within racial/ethnic groups (i). using the equivalence test for paired data (TOST option in the PROC TTEST in R).

(ii). Specific Aim 3. We will develop a recruitment funnel to estimate the number of patients that must be approached to enroll and retain one participant. We will describe adherence to PNP app use, and adherence to the feeding component of the study.

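### The two-hour spacing between eating occasions is written only for Stage 2, so later eating can overlap the Stage 1 test-meal responses that are correlated with the microbiome

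*Protocol*

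**What the plan says.** Protocol 11.1 gives three types of standardized test meal, "each consisting of 50 g of available carbohydrates, given twice to each participant", one each morning from Day 2 to Day 7. Apart from that meal, "participants will be instructed to follow their normal daily routine and dietary habits, except for the first meal of every day". Neither 11.1 nor Table 2 states an interval before the next food or drink.

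Protocol 11.2.2, on the Stage 2 feeding days, does state one: "participants will be directed to leave at least two hours between eating occasions". Its purpose is given in the same sentence: "To ensure that the glycemic response to meals and snack can be detected". The response window is set in 11.4.1: "Observed incremental area under the curve (iAUCobs) at 2 hours following each meal and snack", read from a sensor that records every 15 minutes.

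The test-meal responses have one explicit use in the analysis. In 11.5, "The median PPGR to standardized meals for each participant" is to be related to 16S rRNA, MetaPhlAn and KEGG relative abundances by Pearson correlation.

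**The concern.** The protocol accepts that a 2-hour response needs two clear hours, and it protects the Stage 2 meals accordingly. The Stage 1 test meals have no such protection, although they are the only meals held constant across participants. Someone who takes the test meal and has a snack an hour later has followed every instruction in 11.1, yet the 2-hour area then belongs to two intakes.

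How far this happens will depend on personal habits. The resulting error therefore differs between people, and it enters the variable that 11.5 uses to compare them. There are only two replicates per meal type and 20 participants, so few clean responses are available to offset the affected ones.

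**Working it through.** **Text check.** The protocol was read for any fasting or spacing rule that applies to the test meals.

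| Point | Stage 1 (11.1) | Stage 2 (11.2.2) |
|---|---|---|
| What is fixed | First meal of the day | All meals and snacks |
| Interval between eating occasions | None stated | At least two hours |
| Reason for an interval | None stated | Detecting the response |
| Meals logged in the app | Yes | Yes |

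The count is consistent: 3 types × 2 = 6 test meals over Day 2 to Day 7, which is 6 days.

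**Size for one test meal.** The protocol has no figure to reproduce, so this is an illustration.

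- From the protocol: a 2-hour window with 15-minute readings, so 120/15 + 1 = 9 readings.
- Assumed: excursion g(t) = (t/p)² · exp(2(1 − t/p)), with peak time p of 30, 45, 60 or 75 minutes; a second intake at s minutes with r = 0.5 to 1.0 times the first response; responses that add.
- iAUC = 15 × Σ (yᵢ + yᵢ₊₁)/2 over the nine readings.
- Inflation (%) = 100 × r × iAUC[g(t − s)] / iAUC[g(t)].

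Worked case with p = 60, s = 60, r = 1:

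- Test meal alone: 15 × (0.280 + 0.680 + 0.927 + 1.000 + 0.948 + 0.828 + 0.683 + 0.541/2) = 84.25.
- Added by the second intake: 15 × (0.280 + 0.680 + 0.927 + 1.000/2) = 35.81.
- Inflation: 35.81/84.25 = 42.5%.

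Inflation (%) for r = 0.5 to 1.0:

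| Second intake at | p = 30 | p = 45 | p = 60 | p = 75 |
|---|---|---|---|---|
| 30 min | 47.5–94.9 | 42.2–84.4 | 37.8–75.6 | 34.7–69.4 |
| 60 min | 38.3–76.6 | 27.6–55.1 | 21.3–42.5 | 17.6–35.1 |
| 90 min | 16.3–32.5 | 8.6–17.2 | 5.5–11.0 | 4.1–8.1 |
| 105 min | 4.7–9.4 | 2.1–4.2 | 1.2–2.5 | 0.9–1.7 |
| 120 min | 0 | 0 | 0 | 0 |

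**Size for the variable actually used.** This is a simulation of the median of six test meals. Assumed: peak at 50 minutes, 20% within-person variation, second intake at 30 to 120 minutes, r = 0.5 to 1.0. The median rises by about 5%, 11%, 18% and 25% when 25%, 50%, 75% and 100% of test mornings are affected.

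A Pearson correlation does not change under a proportional shift common to everyone. What matters is how well the observed median still tracks the person's true response, assuming that early eating is unrelated to the microbiome:

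| Between-person log-SD (assumed) | No overlap | 25–100% of mornings affected | Half of participants every morning, half never |
|---|---|---|---|
| 0.40 | 0.97 | about 0.96 | 0.93 |
| 0.25 | 0.94 | about 0.90 | 0.85 |

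Under that assumption a true microbiome correlation shrinks in proportion. In the last column it falls to 0.93/0.97 = 0.96 or 0.85/0.94 = 0.90 of its size without overlap.

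**The case against.** The strongest reply is that little depends on this. Table 2 labels the test meals as the breakfast, so a second breakfast 30 to 60 minutes later is not the natural reading, and the largest figures above rest on the least natural scenario. That stands. A snack or caloric drink inside two hours nevertheless remains within the instruction.

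Meals are time-stamped in the app, and an analysis plan that is not shown may exclude overlapped windows. That also stands in part. But a log finds an overlap only if it was entered accurately, and it cannot restore the lost response. The eating instruction itself belongs in the protocol, which gives it for Stage 2.

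A reader might infer that the test-meal responses calibrate the personal model, so that overlap biases iAUCpred and the equivalence test. The documents do not establish this. Section 10.0 says Stage 1 serves to "conduct metabolic profiling and develop a patient-specific algorithm that predicts glycemic responses to food", and section 3.0 lists a week of monitored glycemia among the original algorithm's inputs, so the link is plausible. Yet the account of model building in 11.1 is to "combine these data with gut microbiome profiles and PNP app derived self-monitoring data to develop an individualized predictive model of glycemic response", and it does not name test-meal responses. None of the figures above measures an effect on iAUCpred.

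A reader might also object that the model is trained without spacing and tested with it. That contrast between free living and controlled feeding is the stated design, and spacing six test meals would not remove it for the other Stage 1 meals.

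**Conclusion.** The point holds as a gap between the protocol's own reasoning and its Stage 1 instruction. A 2-hour response is said to need two clear hours, and the only standardized meals are not given them. The direct effect is person-dependent error in the median PPGR used in 11.5. iAUCobs in Stage 2 is covered by the rule and is not affected.

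A single test-meal iAUC could be inflated by about 18% to 77% by eating at 60 minutes and 4% to 33% at 90 minutes, with nothing added from 120 minutes on. These ranges rest on assumed curve shapes, relative intake sizes and additive responses. How often participants would eat early cannot be derived from the documents. The loss of correlation is probably modest, and the microbiome correlation is not one of the three specific aims. If early eating were itself related to the microbiome, the attenuation figures would not apply. The case for change is that the improvement is nearly free, not that the main comparison is compromised.

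**What to change.** In 11.1 and the participant instructions, extend the existing 11.2.2 spacing instruction to the six Stage 1 test meals: nothing other than water for at least two hours after each, with the start time logged. In 11.5, compute the standardized-meal PPGR only from test meals with no other logged intake within two hours. With a gap of at least 120 minutes, the added area is 0% in every scenario above.

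A further line in 11.1 saying whether test-meal responses enter the personal model would settle the open question about iAUCpred.

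The cost is a few sentences and a filter on app entries already collected. The downside is a slightly less natural morning on six days, and a few test meals may be excluded.

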## 11.2. Stage 2 Feeding Validation\*

#### 10.2.1. Selection of foods for feeding study:

Using the nutrient composition data from derived from the Nutrient Data System for Research, we have established a database of 200 meals that vary in glycemic load (GL). From this database, we will select 60 meals, consisting of 4 breakfast, 4 lunch and 4 dinner meals, and 8 snacks from each of the following categories: low GL, moderate GL, and high GL. Participants will be directed to select 2 meals and 4 snacks from each GL category, or a total of 30 meals and snacks (5/day) that they would be willing to consume during Stage-2. Meals and snacks will be prepared off-site by PortableChef, a foodservice operation in New York City that specializes in tailoring meals and delivering them to clients. Food will be prepared from scratch, portioned to match their estimated energy requirements based on REE or Mifflin St. Jeor equations with a physical activity modifier of 1.3, using a commercial scale (TE10FT, Taylor Precision Products, Inc.; Oak Brook, IL), and delivered to the CTSI-CRC for participants to pick up or to the participant's home (Day-1 and Day-4).

#### 11.2.2. Feeding study:

**Stage-2** feeding will take place on the 8th day Beginning the following day, for 6 days, participants will consume prepackaged meals and snacks. In order to limit the effects of meal order on glycemic response, each meal day will contain a random breakfast, lunch, dinner and 2 snacks from among those selected. The study personnel will call the subject on the 7th day to let the patient know about the feeding phase in detail (Telephone-4). Also, they will discuss about the feasibility and the barrier of using Abbott FGM, PNP app and FitBit. Also, the study personnel will ask the subject to charge the FitBit device. During stage-2 feeding phase, participants will continue to monitor meals, physical activity, sleep, medications, hunger, and stress with the PNP app. We also will obtain FitBit data on physical activity and sleep. A follow-up phone call (Telephone-5) to the subject will be made on to check that the subject is consuming the foods provided by the study and has been able to use the Abbott FGM without any issues. Any AEs or device incidents (DIs) will be recorded. To ensure that the glycemic response to meals and snack can be detected, participants will be directed to leave at least two hours between eating occasions. Although they will be asked to consume all foods and beverages provided, and nothing else (other than water for hydration), participants will be directed to record and report any deviation from the prescribed diet. On the day following the final meal, upon awakening (Day **14**), we will

Protocol version 02/23/2018 Study Protocol: s16-01059 NCT: NCT03053518 call the participants' (Telephone-**6**) and directed to remove the FGM, FitBit devices and return it to the investigators in a postage-paid sharps box provided to them. If the participants did not send the devices within 5 days after the study completion then we will call them 2 additional times (Telephone-**7** and Telephone-**8**).

## 11.3. Measurements

Data are collected with visits to NYU Clinical and Translational Resource Center. Participants are contacted 2 days prior to their appointment to remind them of their measurement visit. Laboratory tests are collected, spun, refrigerated, batched and sent for processing in the CLIA-certified NYU CTSI Translational Research Laboratories by personnel blinded to group assignment. Clinically significant out of range laboratory and/or blood pressure values, as pre-defined by the safety steering committee, will be reviewed by a study clinician and faxed to the treating physician of record for expedited notification. The timing of profiling, measurement, and feeding components are summarized in **Table-2** below.

Table-2	Eligibility		Profiling phase							Feeding Phase							
Procedures	Day: -10	Day: -5	D1	D2	D3	D4	D5	D6	D7	D8	D9	D10	D11	D12	D13	D14	
Visit	1		2														
ELIGIBILITY VISIT																	
Informed consent	$\checkmark$																
HbA1c	$\checkmark$																
Demographics	$\checkmark$																
Indirect calorimetry	$\checkmark$																
(REE)																	
Mailing kit:		✓															
Questionnaires																	
(Background, Physical																	
activity, habits, 3 day																	
food frequency, sleep,																	
medication, general																	
health information)																	
Stool sample																	
collection kit METABOLIC																	
PROFILING																	
Blood chemistry: labs			✓			1											
measurements			•														
Gut microbiota			✓														
Anthropometrics			✓														
FitBit: Sleep and			✓	۲ ۲													
Physical activity																	
PNP app: Lifestyle			✓														
habits																	
Abbott Libre Pro:			✓												✓		
Continuous glucose																	
monitoring																	
Test meals (Breakfast				√					√								
only)																	
CONTROLLED																	
FEEDING																	
Controlled feeding*										

✓

					√		
DEVICE REMOVAL																$\checkmark$	

\*Definition: Participants would be directed to consume only those foods and beverages that are prepared for them in a commercial kitchen, and to avoid eating any non-study food and beverages.

